6.3.5 Adverse events based on signs and symptoms

All AEs spontaneously reported by the patient or reported in response to the open question from the study personnel: Have you had any health problems since you were last asked? or revealed by observation will be collected and recorded in the CRF. When collecting AEs, the recording of diagnoses is preferred (when possible) rather than recording a list of signs and symptoms for example: congestive heart failure rather than low ejection fraction, rales and dyspnea. However, if a diagnosis is known and there are other signs or symptoms that are not generally part of the diagnosis, the diagnosis and each sign or symptom not part of the diagnosis will be recorded separately, for example: congestive heart failure and conjunctivitis.

6.3.6 Adverse Events based on examinations and tests

If laboratory values are judged as clinically significant and/or a treatment has been given for a medical event it will be captured as AEs and if SAE criteria is fulfilled they will also be an SAE.

If vital signs give clinical signs/symptoms and/or require a treatment then they will be captured as AEs and if SAE criteria is fulfilled they will also be SAEs.

Any new or aggravated clinically relevant abnormal medical finding at a physical examination as compared with the baseline assessment will be reported as an AE and if SAE criteria is fulfilled it will also be an SAE.

Wherever possible the reporting investigator uses the clinical, rather than the laboratory term (e.g. anemia *versus* low hemoglobin value).

6.3.7 Follow-up of unresolved adverse events

Any AEs that are unresolved at the patient's last AE assessment in the study are followed up by the investigator until stabilization, for as long as medically indicated or the overall clinical outcome of the patient is known, unless the patient is documented as "lost to follow-up". All SAEs should be followed until the event resolves, stabilizes, or returns to baseline. If the patient is discontinued from the study prior to resolution/stabilization of the SAE, then the patient will be followed as part of the SAE/pharmacovigilance system.

Reasonable attempts to obtain this information must be made and documented. Sponsor retains the right to request additional information for any patient with ongoing AE(s)/SAE(s) at the end of the study, if judged necessary.

6.3.8 Reporting of serious adverse events

All SAEs have to be reported, whether or not considered causally related to the investigational product, or to the study procedure(s). All SAEs will be recorded in the CRF. SAEs will be recorded from the time of admission to the clinic on day 0.

All Serious Adverse Events (SAE) must be reported, whether or not considered related to the study drug, on a separate SAE Report Form. All SAEs will be recorded in the Case Report Form. An assigned CRO will be responsible for reporting all SAEs to regulatory authorities and ethics committees in accordance with ICH Good Clinical Practice and local regulations. As soon as the Investigator is aware of a potential SAE he/she should contact the safety CRO appointed by the sponsor by fax or e-mail and in any case *no later than 24 hours* after the knowledge of such a case. At the time of initial reporting the investigator must provide as a minimum requirement, patient number, birth date, nature of the SAE and a preliminary assessment of causality.

For fatal or life-threatening adverse events where important or relevant information is missing, active follow-up is undertaken immediately. Investigators or other site personnel inform the sponsor and monitor of any follow-up information on a previously reported SAE immediately but no later than within 24 hours of when he or she becomes aware of it. The monitor or sponsor will advise the investigator/study site personnel how to proceed.

The SAE reporting procedures are detailed in the study specific Safety Management Plan. This plan is an agreement between the sponsor and [REDACTED].

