4.1 Overall study design and flowcharts

This is a phase II, open label exploratory study to assess the IdeS efficacy in creating a negative crossmatch test (CXM) in a total of 15-20 patients (7-13 with living donors and 7-13 with a deceased donor) who exhibit DSAs and have a positive crossmatch test to their available live or deceased donors. The first 3 patients in this study will receive a kidney from a deceased donor. The study will primarily examine the efficacy of IdeS in creating a negative CXM in these patients. Included patients will be treated with IdeS on day 0. If it is considered safe and the desired effect is not achieved (negative crossmatch) a second dose can be given within 2 days of the first infusion. In addition to IdeS patients

will be given high dose IVIg (2 g/kg BW, maximum of 140 g) on day 7 and anti CD20 (Rituximab) on day 9 as outlined in [Figure 1](#). DSA levels will be monitored 2, 6, 24 and 48 hours and 7, 14, 21, 28, 64, 90, 120 and 180 days after the last IdeS dosing. Safety, including kidney function will be monitored at multiple time points up to 180 days after treatment. Pharmacokinetics, pharmacodynamics and anti-drug antibodies will be followed. For details on assessments see flow chart in [Table 1](#). Patients who are not eligible for transplantation after IdeS treatment will not be transplanted and thus will not receive any induction therapy or immunosuppression. All patients who receive IdeS will also be asked to remain in the study and be followed up according to the study protocol even if they are not transplanted. In addition, patients who lose their graft during the course of the study will remain in the study and be followed up according to the study protocol.

[figure not shown]

Figure 1. Overall treatment schedule. CXM=crossmatch test, Tx=transplantation.

Table 1. Study flow chart: Screening to Day 180 after IdeS infusion

Study visit	1	2	3	4	5	6	7	8	9	10	11	12
Day	Screening -28-0	0-2	3-6	7	9	14	21	28	64	90	120	180
Assessment /Time window				+/- 1 d	+ 2 d	+/- 2 d	+/- 3 d	+/- 3 d	+/-7 d	+/-7 d	+/-14 d	+/-14 d
Informed Consent	X											
Demographics and medical/surgical history	X	X										
Inclusion/exclusion	X	X										
Physical examination	X											X
Weight	X	X				X						
Height	X											
Vital signs	X	X		X ^c				X		X	X	X
Body temperature	X	X										
CDC and FACS	X	X ^a										
DSAs	X	X		X ^c		X	X	X	X	X	X	X
Pregnancy test (serum)	X	X ^b										X
Adverse events		X	X	X	X	X	X	X	X	X	X	X

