6.3.1 Definition of adverse events

An adverse event (AE) is the development of an undesirable medical condition or the deterioration of a pre-existing medical condition following or during exposure to a pharmaceutical product, whether or not considered causally related to the product. Relationship to the study drug will be deemed as not related, unlikely, possible or probable. An undesirable medical condition can be symptoms (e.g. nausea and chest pain), signs (e.g. tachycardia and enlarged liver) or the abnormal results of an investigation (e.g. laboratory findings and electrocardiograms).

In cases of surgical or diagnostic procedures, the condition/illness leading to such a procedure is considered as the AE rather than the procedure itself.

In case of fatality, the cause of death is considered as the AE, and the death is considered as its outcome.

Pre-treatment adverse event:

A pre-treatment adverse event is any untoward medical occurrence arising or observed between signing of informed consent and the first administration of the IMP.

Treatment emergent adverse event:

A treatment emergent adverse event is any AE occurring after the administration of the IMP and within the time of the follow up period or a pre-treatment adverse event or pre-existing medical condition that worsens in intensity after administration of the IMP and within the time of the follow up period.

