6.3.3 Recording of adverse events

In clinical studies, an AE/SAE can occur at any time after signing of the informed consent until the end of the study, including run-in or washout periods, even if no study treatment has been administered, e.g. and AE can be related to a procedure in the protocol.

AEs will therefore be collected on the AE CRF from the time of signing of the informed consent and throughout the study period including the follow-up period. However, AEs that occur in the time period between informed consent and administration of the trial drug should be recorded as part of the patient's medical history, but will not be considered a treatment emergent adverse event (TEAE) unless directly related to study procedures (e.g. hematoma secondary to laboratory testing) or it meets the definition of an SAE.

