12.2.3 Safety and tolerability

All safety and tolerability data will be listed as specified in the SAP.

Adverse events will be collected for each patient from visit 1 until follow-up. Serious adverse events will be recorded from the time when informed consent is obtained (Visit 1) until the follow-up visit.

The following summaries of AEs will be given by treatment and in total:

The number of patients who had any AEs, SAEs, AEs that led to withdrawal, AEs related to study drug and AEs with severe intensity.

If the number of AEs is sufficiently large, summaries will be presented by PT (Preferred term) and SOC (System organ class) according to MedDRA vocabulary.

Severity, time of onset, duration, action taken, concomitant therapy started and patient outcome of the AEs will be given in data listings only. AEs which were reason for premature discontinuation of study drug will be listed separately.

Furthermore, SAEs and AEs that led to withdrawal will be listed separately.

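### The protocol gives two start points for recording SAEs, so one between consent and day 0 admission may go unrecorded, and its rule on pre-dose SAEs conflicts with its own TEAE definition

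*Protocol*

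**What the plan says.** **Start of SAE recording.** Protocol 6.3.8, on SAE reporting, states: "SAEs will be recorded from the time of admission to the clinic on day 0". Protocol 12.2.3 states: "Serious adverse events will be recorded from the time when informed consent is obtained (Visit 1) until the follow-up visit". Protocol 6.3.3 agrees with 12.2.3. It notes that "an AE/SAE can occur at any time after signing of the informed consent until the end of the study" and continues: "AEs will therefore be collected on the AE CRF from the time of signing of the informed consent". In Protocol Table 1 the adverse-event row has no mark at Visit 1 and begins at Visit 2. The SAP flow chart (SAP 2.1, Table 1) shows the same. The Visit 1 text in Protocol 6.2 does not mention AE collection.

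**Classification of pre-dose events.** Protocol 6.3.3, and the Visit 2 text in 6.2, send events before dosing to the medical history and say they are not TEAEs, "unless directly related to study procedures (e.g. hematoma secondary to laboratory testing) or it meets the definition of an SAE". Protocol 6.3.1 has no such exception: "A pre-treatment adverse event is any untoward medical occurrence arising or observed between signing of informed consent and the first administration of the IMP". It limits TEAEs to events after administration of the study drug, or earlier conditions that worsen after it. SAP 4.5.1 also limits TEAEs to events after administration or later worsening, without an exception for pre-dose SAEs, and plans a separate listing of pre-treatment AEs. SAP section 5, on deviations from the protocol, does not mention that the exception was dropped.

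**The concern.** Collecting SAEs from consent is a patient-safety rule, and the section that sites use to report SAEs gives a later start than the rest of the protocol. A serious event during screening, including one caused by a screening procedure, falls in the gap. Protocol 6.3.4 asks for causality to study procedures to be judged for every SAE, which cannot be done for an event that was never recorded. No analysis rule can recover such an event later, and the pre-treatment listing would be incomplete without any sign of it.

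The classification conflict is a different problem. An event that is recorded correctly can still be treatment-emergent under one protocol section and pre-treatment under another. This can happen within day 0 itself. Premedication is given before the infusion (Protocol 6.1.6), so a serious event after premedication but before study drug falls under both rules.

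**Working it through.** The plan states no figure for this point and plans no hypothesis test, so the check is mainly a comparison of texts.

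**Step 1: start point.** Take a serious event after consent and before admission on day 0.
- Protocol 6.3.8, day-0 sentence: outside the recording window.
- Protocol 6.3.8, duty to report all SAEs regardless of causality: reportable, with no start date attached.
- Protocol 12.2.3 and 6.3.3: inside the window.
- Protocol Table 1 and SAP Table 1: no AE assessment marked at Visit 1. Table 2 in both documents marks one at pre-dose.

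The day-0 and consent start points cannot both apply, and 6.3.8 alone can be read either way.

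**Step 2: length of the gap.** Screening runs from day -28 to day 0 (Protocol 6.2, Table 1), so the gap is at most 28 days per screening. Protocol 5.1 allows re-screening of an eligible patient who was not dosed within 28 days, for example for want of an organ offer, so the total can exceed 28 days. It can also be close to zero for a patient who consents shortly before dosing.

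**Step 3: classification.** Suppose the event is recorded, does not worsen after dosing, and the patient is dosed.
- Protocol 6.2 and 6.3.3: TEAE, because the exception reads "or it meets the definition of an SAE".
- Protocol 6.3.1: pre-treatment AE.
- SAP 4.5.1: not a TEAE; it goes to the pre-treatment listing.

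The SAP is not fully clear either. Its overview row equates SAEs with serious TEAEs, while its further SAE tables do not say whether pre-dose SAEs count.

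**Step 4: size.** Let N be the number of dosed patients (planned 15 to 20) and k the number with at least one serious TEAE under the SAP definition.
- Pre-dose SAE lost, SAP definition applied: the proportion stays k/N, a shift of 0. The pre-treatment listing lacks one entry.
- Pre-dose SAE recorded, SAP definition applied: the shift is again 0, and the listing is complete.
- Pre-dose SAE counted as treatment-emergent, patient not already in k: k/N becomes (k+1)/N. The shift is 1/N, from 1/20 = 5.0 to 1/15 = 6.7 percentage points.
- Same, but patient already in k: the patient-level shift is 0.
- Pre-dose SAE in a screened patient who is never dosed: no effect on these tables, because the safety set contains only dosed patients (SAP 3.1).

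**The case against.** The strongest reply on capture is that 6.3.8 is not a clean instruction to omit. It says that all SAEs have to be reported, whatever their cause, and that all go into the CRF. Protocol 6.3.3 is the section titled for recording and starts at consent, and 6.3.4 has seriousness recorded for each AE. Detailed procedures are left to a Safety Management Plan that is not among these documents, so actual site practice is unknown. The blank Visit 1 cell is weak evidence by itself: consent is signed at that visit, and the next contact is where events since then would naturally be asked about. All of this stands. It makes loss a risk and not a certainty, but it does not remove the day-0 sentence, which sits in the same section as the general duty and can be read as setting its window.

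On classification, the reply is that the SAP definition keeps pre-dose SAEs out of the TEAE tables and lists them separately. This also stands. A reader might go further and infer that the database will disagree with the SAP on which SAEs are treatment-emergent. The documents do not support that: the AE variables in Protocol 6.3.4 include no treatment-emergent field, and the SAP builds its analysis data from the exported data. What remains is a conflict of wording between the protocol and the SAP, and within the protocol.

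**Conclusion.** The protocol contradicts itself on when SAE recording starts, and the contradiction should be removed. The exposure is limited to the time between consent and day 0 admission: up to 28 days per screening, longer with re-screening. The documents give no expected rate of SAEs in that period, so the number at risk cannot be estimated.

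The classification conflict is real but largely contained. If the SAP definition is applied, the TEAE tables do not change. The shift of 5.0 to 6.7 percentage points needs all of the following: the patient was dosed, had a pre-dose SAE, had no other serious TEAE, and had that SAE counted as treatment-emergent. It also takes the planned 15 to 20 patients as the denominator.

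Three stronger readings are tempting and do not hold. One is that a site following 6.3.8 would miss every SAE after consent; at most it misses those before admission on day 0. Another is that SAEs have in fact been lost; the documents do not show this. The third is that a lost pre-dose SAE moves the reported SAE proportion by 5 to 7 points; under the SAP definition it moves it by nothing. The primary endpoint is not affected. This is an internal inconsistency that should be corrected, at the lower end of that grade.

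**What to change.** 1. In Protocol 6.3.8, replace the day-0 start with signing of informed consent, in line with 12.2.3 and 6.3.3.
2. Mark the adverse-event row at Visit 1 in Table 1 of both the protocol and the SAP.
3. In Protocol 6.2 (Visit 2) and 6.3.3, reword the whole sentence on pre-dose events. State that pre-dose SAEs and procedure-related events are recorded on the AE/SAE forms as pre-treatment events, neither as TEAEs nor only as medical history. Deleting just the exception is not enough: it would leave the instruction to record pre-dose events as medical history, with nothing to set SAEs apart.
4. If enrolment is already complete, an amendment cannot recover missed events. SAP 4.1 describes dosing in the past tense, so this may be the case. The data review before database lock (SAP section 3) should then check for SAEs between consent and dosing, including on the medical-history pages, and list any found separately.

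The cost is one sentence in 6.3.8, one sentence reworded in two places, one table cell in each document, and possibly a few more pre-dose SAE reports. Step 4 adds one item to a review that is already planned.

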6.3.9 Reporting of suspected unexpected serious adverse events (SUSARs)

A suspected serious adverse reaction is any serious adverse event for which there is a reasonable possibility that the investigational product caused the adverse event. A serious adverse reaction is considered "unexpected" if it is not listed in the investigator brochure or is not listed at the specificity or severity that has been observed.

SUSAR MedWatch reports **WILL NOT** be filled out for any prolonged hospital admissions or readmissions that are related to expected complications of the patients' primary

disease (CKD). For example, prolonged admissions for dialysis or readmission for fluid overload as a consequence of CKD since this is an expected complication of the patients' disease state and not related to study drug. These events will be adjudicated by the PI. Otherwise, all SUSAR MedWatch reports will be submitted to the IRB, study sponsor and FDA.

SUSARs with an outcome of death or are life threatening must be reported to the relevant regulatory authorities within 7 calendar days, all other SUSARs must be submitted within 15 calendar days. The SUSAR reporting procedures are detailed in the study specific Safety Management Plan. This plan is an agreement between the sponsor, and [REDACTED] will notify the appropriate regulatory agency(ies) of any SUSARs on an expedited basis and in accordance with applicable regulations. Sponsor will notify all participating site Investigators. In addition the sponsor is responsible for informing all investigators in all ongoing studies involving IdeS about all SUSARs.

It is the responsibility of the site Investigator to promptly notify the IRB and other appropriate institutional regulatory bodies of all unexpected serious adverse reactions involving risk to human subjects as per their applicable requirements.

6.3.10 Procedures in case of pregnancy

Pregnancy is an exclusion criteria and a pregnancy test is performed twice before the study drug is infused; at the screening visit and prior to infusion of the IMP. A pregnancy test is also performed at the last study visit.

If a patient becomes pregnant during the follow up phase of the study, the patient will continue in the study according to study protocol, if possible. A Pregnancy Report Form must be sent by Principal Investigator to sponsor (or designee) at the latest within 24 hours of learning of the pregnancy. The outcome of all pregnancies (spontaneous miscarriage, elective termination, normal birth or congenital abnormality) will be followed up on the Pregnancy Report Form even after the patient has completed or discontinued the study. Sponsor (or designee) will follow up on pregnancy outcome 4 weeks after the projected due date.

Pregnancy itself is not considered an AE or SAE, but any event occurring during pregnancy that meets serious criteria must be reported to sponsor and will be handled as a SAE. Spontaneous abortions, congenital abnormalities/birth defects are always considered to be a SAEs and will be reported and followed up in accordance with other SAEs. Any SAE occurring as a result of a post-study pregnancy and considered reasonably related to the study drug by the investigator will be reported to the sponsor (or designee).

6.4 Study assessments

6.4.1 Recording of data

The principal investigator will provide the sponsor with all data produced during the study from the scheduled study assessments. He/she ensures the accuracy, completeness, legibility, and timeliness of the data reported to sponsor in the CRF and in all required reports. The study assessments are described in the sections below and the timing of these assessments are detailed in the study flow charts (Table 1 and Table 2). It is important that PK sampling occurs as close as possible to scheduled time. In order to achieve this, other assessments scheduled at the same time may be initiated prior to the time point. Pre-dose assessments may be performed up to 60 minutes prior to dosing.

The timing priority order at a particular time point is:

1. Blood samples for PK and PD
2. Samples for DSA, CDC and FACS CXM
3. Vital signs
4. Safety laboratory samples
5. Additional laboratory samples

Pre-dose assessments may be performed up to 60 minutes prior to dosing.

6.4.2 Screening and demography procedures

Each patient will undergo a screening between 28 and 0 days prior to admission.

6.4.3 Patient care after end of study

After study completion, all study patients will be followed up regularly and interdisciplinary (by nephrologist and transplant surgeons) according to the center's follow-up routines for transplanted patients. The frequencies of outpatient visits will be adjusted individually to the state of patient health and transplant function.

6.5 Laboratory efficacy assessments and evaluation of primary endpoint

Timing of laboratory efficacy parameters (CDC and FACS crossmatch tests and DSA analysis) is given in the study flow charts 1 and 2 ([Table 1](#) and [Table 2](#)). The date and time of collection will be recorded on the laboratory requisition form and in the CRF. Samples will be labelled, stored and shipped as detailed in the laboratory manual.

6.5.1 Analysis of crossmatch tests

Evaluation of the primary endpoint will be analyzed using the crossmatch test. CDC and flow cytometry (FACS) crossmatch test will be performed at the time points indicated in the study flowcharts ([Table 1](#) and [Table 2](#)).

